8.4.2 Unblinding procedures

The blind for all personnel involved in this clinical investigation will not be broken until the Blind Data Review Meeting (BDRM) has convened, the Statistical Analysis Plan (SAP) has been finalized, and the database has been locked. The statistical analysis will proceed after the unblinding, which will be documented.

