12.4.5.4 Discontinuations and Missing Data

Besides the analyses based on observed data, additional sensitivity analyses for primary and secondary effectiveness endpoints will be carried out with missing data imputed using single value imputation methods. Imputations will be performed until Month 6.

Missing effectiveness data and missing safety data will be imputed as follows:

Effectiveness:

Worst Case Scenario (WCS):

• For the WCS method, missing post-baseline data for Radiesse treatment group will be imputed as non-responders, while missing post-baseline data for Restylane treatment group will be imputed as responders. As a result, the WCS is considered a conservative imputation method because missing values from the control are imputed as responders while missing values from the treatment are imputed as non-responders. The WCS will be used for sensitivity analysis.

Further imputation methods will be described in the SAP.

Safety:

Each medication/therapy will be allocated unambiguously either to previous medications or to concomitant medications.

- If stop date is before start of treatment: Previous medication
- If the stop date is at or after start of treatment or ongoing is checked: Concomitant medication
- Otherwise, if the stop date is missing or partially given:
 - Partial stop date available: Previous therapy if the latest possible stop date is before start of treatment; Concomitant therapy if the latest possible stop date is at or after start of treatment
 - If the stop date is completely missing: Concomitant therapy

Each finding will be allocated unambiguously either to medical history or to concomitant diseases.

- If the stop date is before start of treatment: Medical history
- If the stop date is at or after start of treatment or ongoing (even if it refers to a cut-off point before start of treatment) is ticked: Concomitant disease
- Otherwise, if the stop date is missing or partially given:
 - Partial stop date available: Medical history if the latest possible stop date is before start of treatment; Concomitant disease if the latest possible stop date is at or after start of treatment
 - Stop date is completely missing for findings coded as "Surgical and medical procedures": Medical history
 - Stop date is completely missing for other findings: Concomitant disease

For AEs, imputation of missing start or stop dates will follow the steps below:

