theta=e/ (e+f)-g/ (g+h) ;
d12=(e+f) /n-12;
du2=u2- (e+f) n;
d13=(e+g) /n-13;
du3=u3- (e+g) /n;
if e*h>f*g then phi=max (e*h-f*g-n/2,0) ;
else if (e+f) *(g+h) *(e+g) *(f+h)=0 then phi=0;
else phi=(e*h-f*g)/sqrt ((e+f) *(g+h) *(e+g) *(f+h));
delta=sqrt (d12**2-2*phi*d12*du3);
epsilon=sqrt (du2**2-2*phi*du2*du3+d13**2);
L=theta-delta;
U=theta+epsilon;
```

		Response with Restylane		
		yes	no	total
Response with Radiesse	yes	e	f	
	no	g	h	
	total			n

The confirmatory analysis will be based on the PPS using observed values only.

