7.4 Special Statistical/Analytical Issues

7.4.1 Discontinuations and Missing Data

Effectiveness:

Besides the analyses based on observed data, additional sensitivity analyses for primary and secondary effectiveness endpoints will be carried out with missing data imputed using single value imputation methods. Imputations will be performed until Month 6.

Missing effectiveness data will be imputed as follows:

Worst Case Scenario (WCS):

- For the WCS method, missing post-baseline data for Radiesse treatment group will be imputed as non-responders, while missing post-baseline data for Restylane treatment group will be imputed as responders. As a result, the WCS is considered a conservative imputation method because missing values from the control are imputed as responders while missing values from the treatment are imputed as non-responders. The WCS will be used for sensitivity analysis. As this method is an extreme conservative method, an additional, probably more realistic but still conservative imputation method will be performed based on pattern (reason) of missingness:
- *Pattern Based Scenario (PBS):* At the BDRM, the reasons for subjects' withdrawals before Month 1, Month 3 or Month 6 assessment of the WSRS and/or GAIS assessment (with the consequence that these values are missing) are reviewed and assessed as "probably missing at random" or as "definitely or possibly missing not at random". Hereby "Lost to follow-up" will be assessed as "probably missing at random", while "AE related to treatment" will be assessed as "definitely or possibly missing not at random". For subjects with an assessment of "probably missing at random", no imputation will be performed. For subjects with an assessment of "definitely or possibly missing not at random", it will be checked whether the withdrawal is related to only one of the two treatments (this is the case if e.g. the AE leading to WD is located on one face side only). If so, the subject is treated as "non-responder" for this treatment and as "responder" for the other. If not, the subject is treated as "non-responder" for both treatments.

Safety:

Each medication/therapy will be allocated unambiguously either to previous medications or to concomitant medications.

- If stop date is before start of treatment: Previous medication
- If the stop date is at or after start of treatment or ongoing is checked: Concomitant medication
- Otherwise, if the stop date is missing or partially given:

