Statistical analyses will be performed when all subjects reach the 6 Month post initial injection time point. Primary effectiveness variable, secondary effectiveness variables and AE data will be analyzed using the snapshot of data for the first 6 months. A Statistical and a Clinical Study Report will be generated for the aforementioned analysis. They will be amended by a description and discussion of the analyses performed when all subjects have completed the study. For further details on which tables are produced for the Clinical Study Report and which for the amendment, please refer to the TFLs.

No examination for early termination is planned.

7.4.3 *Data Monitoring Committee*

There will be no data monitoring committee for this study.

7.4.4 *Multiple Comparisons/Multiplicity*

Only the analysis of the primary effectiveness endpoint based on PPS using observed values is of confirmatory nature. Further analyses on the primary effectiveness endpoint are performed for sensitivity reasons. Analyses of all other endpoints/variables is of exploratory nature.

7.4.5 *Examination of Subgroups*

No subgroup examination will be performed for this study.

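### The SAP calls its Pattern Based Scenario conservative, but only one of its four rules reliably is, and no graded analysis lies between it and the worst case

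*SAP*

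**What the plan says.** SAP 7.4.1 sets two single-value imputation analyses beside the observed-value analysis.

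- **WCS** makes every missing Radiesse fold a failure and every missing Restylane fold a success. The SAP grants that this is severe ("As this method is an extreme conservative method") and on that ground adds a second method.
- **PBS** is introduced as a "probably more realistic but still conservative imputation method will be performed based on pattern (reason) of missingness". Reasons for withdrawal are classified at the blind data review. Where data are judged likely to be missing at random, and loss to follow-up is placed there in advance, "no imputation will be performed". For the rest, "it will be checked whether the withdrawal is related to only one of the two treatments". If so, the fold concerned is a failure and the opposite fold a success, whichever product is involved. If not, both folds are failures.

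SAP 7.1.1 states: "The confirmatory analysis will be based on the PPS using observed values only". SAP 7.4.4 gives the other analyses a supporting role: "Further analyses on the primary effectiveness endpoint are performed for sensitivity reasons". Protocol 12.4.5.4 names WCS only and adds: "Further imputation methods will be described in the SAP". The readable text of both documents contains no tipping-point or other graded method.

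**The concern.** In a non-inferiority trial, a conservative imputation is one that makes the claim harder to reach. The PBS rules are written symmetrically for the two products, which may be sensible, but symmetry is not conservatism when the question is one-sided.

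The likely difficulty is a report in which the observed-value analysis and PBS pass and WCS fails. WCS could be set aside as extreme on the SAP's own words, and robustness would then rest on PBS. Depending on why subjects withdrew, PBS may have applied no stress, or may have been easier to pass than the analysis it is meant to check. Nothing pre-specified would show how unfavourable the missing data must be before the claim is lost.

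**Working it through.** **Inputs from the documents.** Margin 10 points, judged by the lower limit of the two-sided 95% Newcombe paired interval (SAP 7.1.1). Discordance 17.5%, 138 evaluable, about 174 randomized, a combined 20% attrition (SAP 4).

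**Assumptions.** The documents give no response rate, number missing or mix of reasons. I take Restylane response 80% (range 60-90%), discordance 17.5% (range 15-25%), and 9 of 174 missing, so 165 observed pairs; 3 missing is also tried.

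**The plan's own figure.** n = (1.960 + 0.842)² × 0.175 / 0.10² = 7.849 × 17.5 = 137.4, so 138. Then 138 / 0.8 = 172.5, close to 174. Both reproduce.

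**Interval.** With e, f, g, h as in the SAP table (both respond, Radiesse only, Restylane only, neither), D = (f - g)/n and

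L = D - √(dl₂² - 2φ·dl₂·du₃ + du₃²), with φ = max(eh - fg - n/2, 0) / √[(e+f)(g+h)(e+g)(f+h)] when eh > fg.

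This is the standard form. The SAP prints φ for this case without its denominator.

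**Example.** e, f, g, h = 118, 14, 14, 19, so n = 165 and both sides respond in 132/165 = 80%. The Wilson limits are 73.25% (Radiesse, lower) and 85.39% (Restylane, upper), so dl₂ = 0.0675 and du₃ = 0.0539. φ = (2242 - 196 - 82.5)/4356 = 0.451. The square root is 0.0647, so L = -6.5%.

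**How each rule enters.** A both-side failure adds 1 to h, a Restylane-side withdrawal adds 1 to f, and a Radiesse-side withdrawal adds 1 to g. Loss to follow-up adds nothing. WCS adds all missing subjects to g.

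| Scenario | 118,14,14,19 (D = 0) | 118,12,16,19 (D = -2.4%) |
|---|---|---|
| Observed | -6.5% | -8.9% |
| 9 both-side | -6.1% | -8.4% |
| 3 Restylane-side | -4.9% | -7.3% |
| Radiesse-side | -8.4% (3 subjects) | -10.2% (2 subjects) |
| WCS, 9 missing | -12.1% | -14.4% |

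A both-side failure leaves f - g alone and enlarges n, which pulls D towards zero. In tables of 138 pairs with 24 discordant, adding ten such pairs raised the limit for observed D up to +5.8% and lowered it from +8.7% upwards, where non-inferiority is not in doubt.

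**All tables.** Of the 776,216 possible tables of 165 pairs, 403,566 pass on observed values. No mix of up to nine both-side and Restylane-side withdrawals overturns any of them. One Radiesse-side withdrawal overturns 6,394 and raises the limit in none.

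**Rates.** Exact multinomial enumeration with cell probabilities f = (0.175 + D)/2, g = (0.175 - D)/2, e = 0.80 - g, h the remainder. At true D = 0 the observed-value analysis passes in 85% of trials and WCS in 24%. Among observed-value passes:

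| Both / Radiesse / Restylane | PBS limit above observed | Overturned by PBS | Mean shift (points) |
|---|---|---|---|
| 9/0/0 | 97.5% | 0% | +0.32 |
| 6/0/3 | 100% | 0% | +1.75 |
| 7/1/1 | 78% | 0% | +0.11 |
| 3/3/3 | 0.4% | 0.2% | -0.28 |
| 8/1/0 | 0% | 1.0% | -0.36 |
| 2/1/0 plus 6 lost to follow-up | 0% | 4.4% | -0.59 |
| 6/3/0 | 0% | 15% | -1.71 |

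For 9/0/0, the 97.5% ranges over 96-98% across the 18 feasible combinations of the response rates and discordances tried. PBS passes while WCS fails in 72% of observed-value passes (69-73%). With 3 missing, all both-side, that figure is 18% (15-23%).

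**Type I error.** At true D = -10% the observed-value analysis passes in 2.7%. PBS alone would pass in 4.2% (9/0/0) or 10.0% (6/0/3), but both pass in only 2.7%. Because PBS cannot make the claim, there is no inflation.

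**The case against.** The best counter-argument is that the PBS one-side rule applies equally to both products, so a balanced mix is a natural reference case. There PBS behaves as the SAP says: with 3/3/3 or 1/1/1 it is stricter than observed values in more than 99% of passing trials. This stands, and it means PBS can be lenient, not that it usually is. It does not rescue the label, since 7/1/1 is also balanced between the products and is lenient in 78%.

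Second, the 72% is mostly a fact about WCS: it is 71.6% under the stricter 3/3/3 mix. That also stands. The figure shows the width of the gap between the two imputations, not how lenient PBS is.

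Third, the both-side effect is small: a mean of +0.11 points with three such failures and +0.32 with nine. Nine is an assumption. It is also close to definitional that PBS cannot overturn a pass once Radiesse-side withdrawals are removed. Both are fair; the finding is about direction and absence of stress, not a large bias.

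Fourth, the calculations treat all 165 non-missing subjects as the observed analysis and ignore exclusions for major deviations. The rates would shift in a smaller set, but the direction of each rule was the same in tables of 138 pairs.

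Finally, there are safeguards: classification at the blind data review, WCS as a bound, planned paired cross tables, and tabulated withdrawals. A reader could work out a tipping point from these by hand. None of this is a pre-specified graded analysis, and none corrects the stated property.

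**Conclusion.** The point holds. The SAP attributes to PBS a property that its rules do not guarantee: only the Radiesse-side rule reliably makes non-inferiority harder to show. The net direction depends on the withdrawal mix. In the mixes examined, the mean shift in the lower limit ran from +1.75 points (6/0/3) to -1.71 points (6/3/0). These sizes rest on assumed response rates, discordance and counts of missing subjects. The direction of the two one-side rules does not. The direction of the both-side rule holds when the limit is near the margin and can reverse when it is well above zero.

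The confirmatory result, its type I error and the sample size are untouched. The harm is confined to how convincingly the trial can show that its result withstands missing data. That is enough to warrant a change before unblinding.

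**What to change.** Protocol 8.4.2 keeps the blind until, among other steps, "the Statistical Analysis Plan (SAP) has been finalized, and the database has been locked", and Protocol 12.4.5.4 leaves further methods to the SAP, so this can be done in the SAP alone.

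1. Remove the claim that PBS is conservative. Describe it as a reason-based scenario whose direction depends on the mix of withdrawals.
2. Report the number of subjects under each of the four PBS rules.
3. Pre-specify a tipping-point grid. For the M subjects with missing Month 6 WSRS, give the lower 95% limit for every combination of 0 to M assumed Radiesse successes and 0 to M assumed Restylane successes. State how successes are paired within subjects, mark where the limit crosses -10%, and label the WCS corner.

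The two example tables with M = 9 show what the grid adds. In the first, the claim is lost only when assumed Restylane successes exceed Radiesse successes by 6 or more (-10.1% at six), whether concordant or discordant pairs are filled first. In the second, it is lost at an excess of 3 with concordant pairs filled first, but four cells already fail at 2 with discordant pairs filled first. That is why the pairing rule must be fixed in advance.

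The cost is a few lines of SAP text, one count table and one short program. The sensitivity picture may look less favourable than PBS alone would make it.

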7.2 Safety Endpoints

All safety analyses will be performed on the SES.

The assessment of safety will be based mainly on the frequency of adverse events.

Only treatment-emergent AEs (TEAEs) will be analyzed, which are defined as AEs with onset or worsening after the first administration of Restylane or Radiesse.

TEAEs will be summarized for each treatment group (as applicable) by the incidence of at least one event, the number of events, and the incidence using Medical Dictionary for Regulatory Activities (MedDRA) version xxx preferred terms within the system organ classes (SOCs). The detailed information on AE including the outcome will be listed.

In case of missing intensity or missing causal relationship of an AE the worst case principle will be applied, i.e. a missing intensity will be set to “severe” and a missing causal relationship will be set to “related”.

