 - Partial stop date available: Previous therapy if the latest possible stop date is before start of treatment; Concomitant therapy if the latest possible stop date is at or after start of treatment
 - If the stop date is completely missing: Concomitant therapy

Each finding on the medical history page will be allocated unambiguously either to medical history or to concomitant diseases.

- If the stop date is before start of treatment: Medical history
- If the stop date is at or after start of treatment or ongoing (even if it refers to a cut-off point before start of treatment) is ticked: Concomitant disease
- Otherwise, if the stop date is missing or partially given:
 - Partial stop date available: Medical history if the latest possible stop date is before start of treatment; Concomitant disease if the latest possible stop date is at or after start of treatment
 - Stop date is completely missing for findings coded as “Surgical and medical procedures”: Medical history
 - Stop date is completely missing for other findings: Concomitant disease

For AEs, imputation of missing start or stop dates will follow the steps below:

[figure not shown]
- If the start date (and time, if applicable) is partially missing but implies start before start of treatment or after date of final examination, the AE will be considered as Non-Treatment Emergent Adverse Event (TEAE).
- If the start date (and time, if applicable) is partially missing and possibly after start of treatment and before or after date of final examination, will be considered as TEAE.

AEs with completely missing onset dates will be considered treatment emergent; no estimation of the dates will be performed.

For the imputed analysis start date of adverse events (variable ASTDT) in the ADaM domain ADAE the following imputation rules related to any treatment period will be used if applicable:

Figure 1: Possible start/end dates of AEs

1. Available start and end information clearly indicates that the AE started and/or ended before first injection -> non treatment emergent

2. Available start and end information does not clarify whether the AE started before first injection or at any timepoint thereafter
-> imputed start = date of first injection -> TEAE for cycle 1

3. Available start and end information indicates that AE started after first injection -> imputed start = first possible date after first injection
-> TEAE for preceding injection

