1a) If the start date is missing completely and the end date and time* does imply end before first injection then no imputation of start date and time will be performed.

1b) If the start date is partially missing and the partially missing start date and/or the end date and time* do imply start and/or end before first injection then set missing start day to 1 / missing start month to 1, if applicable and set start time (if not available) to 23:59, if not after end date/time (else set start time to end time) (e.g. start date of AE: 2008-11 end date of AE: 2009-02-01, end time 22:00 and first injection: 2008-12-06 T17:35 → imputed start date: 2008-11-01, start time: 23:59). Set imputation flags accordingly.

2a) If the start date is missing completely and end date and time* do not imply end before first injection then set imputed start date to date of first injection and set start time (if not available) to 23:59, if not after end date/time (else set start time to end time). (e.g. start date of AE: missing, end date of AE: 2008-12-31, end time 23:00, first injection date: 2008-12-06T17:35 → imputed start date: 2008-12-06, start time: 23:59). Set imputation flags accordingly.

2b) If the start date is partially missing and the non-missing part is the same as in first injection date and the end date and time* do not imply end before first injection, then set the imputed start date to the first injection date and set start time (if not available) to 23:59, if not after end date/time (else set start time to end time) (e.g. start date of AE: 2008-12, end date of AE: 2008-12-31, end time 23:00, first injection date: 2008-12-06T17:35 → imputed start date: 2008-12-06, start time: 23:59). Set imputation flags accordingly.

3) If the start date is partially missing and imputation rule 1b and 2b do not fit, then set missing day to 1 / missing month to 1, if applicable and set start time (if not available) to 23:59, if not after end date/time (else set start time to end time) (e.g. start date of AE: 2009-02 end date of AE: 2009-02-01, end time 22:00 and first injection: 2008-12-06 T17:35 → imputed start date: 2009-02-01, start time: 22:00). Set imputation flags accordingly.

End date or end time will not be imputed.

* The end date and time may be available completely, partly or may be missing.

7.4.2 *Interim Analyses*

In the mock shells it is specified for each table/listing whether it is to be produced for the interim report and/or amendment.

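### For AEs with a missing or partial start date, the SAP's treatment-emergence rules contradict each other and the SAP's own TEAE definition

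*SAP*

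**What the plan says.** SAP 7.2 restricts the AE analysis to TEAEs, "which are defined as AEs with onset or worsening after the first administration of Restylane or Radiesse". SAP 7.4.1 then gives two sets of rules for AEs with incomplete dates.

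**Text rules** (also in protocol 12.4.5.4):
- First partial-date bullet: if the start date "is partially missing but implies start before start of treatment or after date of final examination, the AE will be considered as" non-emergent.
- Second partial-date bullet: an AE whose start date "is partially missing and possibly after start of treatment and before or after date of final examination, will be considered as TEAE".
- Onset wholly missing: "AEs with completely missing onset dates will be considered treatment emergent; no estimation of the dates will be performed".

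**Figure 1 on AE start and end dates, and rules 1a to 3** (SAP only, for the analysis start date ASTDT):
- Item 1: "Available start and end information clearly indicates that the AE started and/or ended before first injection -> non treatment emergent".
- Rule 1a: "If the start date is missing completely and the end date and time* does imply end before first injection then no imputation" of the start is made.
- Rule 1b: for a partial start, where the start or the end lies before injection, the missing day or month is set to 1.
- Rule 2a: where onset is wholly missing and the end is not shown to precede injection, "then set imputed start date to date of first injection".

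Protocol 10.6 collects AEs from signature of the consent form. Protocol 9.2.2 lets screening begin at Day -14. Protocol 10.6.1 lists the date of worsening among the items that must be recorded for each AE.

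**The concern.** The text rules look only at the start date. Figure 1 and rules 1a to 3 look at start and end dates. Neither set looks at the date of worsening, which is part of the TEAE definition. Where they disagree, a programmer has no stated order of precedence, and two programmers could produce different TEAE tables from the same data.

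The two possible errors run in opposite directions. The missing-onset sentence and the second bullet can bring in an AE that was over before any product was injected. The first bullet and item 1 can leave out an AE that got worse after injection. Evaluating safety is one of the two stated study aims, and AE incidence is its endpoint, so membership of the TEAE set should not depend on which paragraph is read.

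**Working it through.** No sample size or error rate is involved. The check applies each rule set to the same AE records and compares the classifications.

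**Inputs.** First injection is 2008-12-06, as in the SAP's worked examples. The definition is SAP 7.2: "AEs with onset or worsening after the first administration of Restylane or Radiesse". A final examination date of 2009-12-06 was assumed and changes none of the results.

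**Step 1: the SAP's own examples.** The imputed start dates reproduce: rule 1b gives 2008-11-01, rule 2a gives 2008-12-06, rule 2b gives 2008-12-06 and rule 3 gives 2009-02-01. In all four, the text rules and Figure 1 agree on emergence (non-TEAE for 1b, TEAE for the others). The worked examples therefore do not expose the conflict.

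**Step 2: illustrative cases that the examples do not cover.**

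| Case | Onset | End | Worsened | Text rules | Figure 1 and rules 1a to 3 | SAP 7.2 definition |
|---|---|---|---|---|---|---|
| A | missing | 2008-12-03 | none | TEAE | non-TEAE (item 1); no start imputed (1a) | non-TEAE |
| A2 | 2008-12 | 2008-12-03 | none | TEAE (second bullet) | non-TEAE (item 1); start 2008-12-01 (1b) | non-TEAE |
| B | 2008-11 | 2009-02-01 | 2008-12-20 | non-TEAE (first bullet) | non-TEAE (item 1) | TEAE |
| B2 | 2008-11-28 | 2009-02-01 | 2008-12-20 | not applicable (date complete) | non-TEAE if item 1 is read literally | TEAE |

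**Step 3: reading the table.**
- In A and A2 the AE ended three days before injection, so it cannot have begun or worsened after injection. Item 1 agrees with the definition and the text rules do not.
- In B both rule sets agree with each other and both depart from the definition, because neither refers to the date of worsening.
- In B2 the onset date is complete, so nothing needs imputing and SAP 7.2 applies. Only the literal wording of item 1 points the other way.

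**Step 4: the clause against estimating dates.** Rule 2a does assign a start date when onset is missing. For those AEs the missing-onset sentence and rule 2a both lead to TEAE, so the clash is one of wording and changes no classification.

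**The case against.** The case for leaving the rules alone has several parts.

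- **Scope.** The rules stand under imputation of missing dates, and Figure 1 serves the imputed analysis start date. A reader might infer that every AE that began in screening and worsened after injection is lost from the TEAE tables. The documents do not support that: with a complete onset date the definition in SAP 7.2 governs. The worsening conflict is firm only for a partial onset date that implies a pre-injection start. This limit stands.
- **The SAP's example for rule 1b.** A reader might take it as a misclassified event because it continues after injection. It contains no worsening, and continuing past injection does not make an AE treatment emergent under SAP 7.2. Its classification is correct.
- **Recording practice.** If a worsening were entered as a new AE with its own start date, the worsening conflict would disappear. The documents do not state such a convention, and they ask for a date of worsening within the AE record.
- **Rarity and direction.** Onset date is a required item, AEs are assessed at every visit, and the pre-injection window is at most about 14 days and may be nil when screening and baseline share a day. Over-counting in cases A and A2 is conservative for safety, and AE details are listed in any case. All of this limits the consequence. It does not remove the contradiction, and case B errs in the other direction.

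**Conclusion.** Wrong as written, for AEs with missing or partial start dates. An AE that ended before first injection is a TEAE under the missing-onset sentence or the second partial-date bullet and a non-TEAE under Figure 1 item 1, and only the latter fits SAP 7.2. An AE with a partial pre-injection onset that later worsens is excluded by the first bullet and by item 1, although SAP 7.2 includes it.

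The effect is on TEAE counts only. It is likely small, but the documents give no number of AEs with incomplete dates, so it cannot be quantified. The conclusion on worsening assumes that a worsening is recorded within the original AE record, as protocol 10.6.1 suggests. The conclusion on AEs that ended before injection needs no such assumption.

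**What to change.** In SAP 7.4.1 and protocol 12.4.5.4:

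1. Replace the missing-onset sentence and amend the second partial-date bullet to the effect of: *An AE with a missing or partial onset date is treatment emergent if it could have started after the first injection, unless its end date shows that it ended before the first injection.* The clause on a start after the final examination can stay as it is.
2. Add to the first partial-date bullet, and to Figure 1 item 1 in the SAP: *unless the recorded date of worsening is after the first injection, in which case it is a TEAE.* For complete onset dates this only brings item 1 into line with SAP 7.2.
3. Replace the clause against estimating dates with a reference to rules 1a and 2a for ASTDT.

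The imputation of ASTDT itself need not change. If the eCRF convention is to enter a worsening as a separate AE, the SAP should say so.

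The cost is a few sentences and a small change to the ADAE program. The date of worsening is already collected, so no new data are needed.
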